**Aim 1: Evaluate RIMO's direct effect on linkage to MAT, length of time on MAT, dropout, and total days of MAT.**

H1: Relative to the control group, RIMO will have a direct effect on: a) initiating MAT sooner, b) staying on medication longer, c) reducing dropout, and d) receiving more total days of MAT.

**Aim 2: Evaluate RIMO's direct and indirect (via MAT) effects on time to relapse, opioid use, and opioid-related overdose.**

H2: RIMO will have direct and indirect (via days of MAT treatment) effects on: a) time to relapse, b) days of opioid use, and c) number of overdoses.

**Aim 3: RIMO's direct and indirect (via MAT and opioid use) effects on opioid-related fatalities, OUD symptoms, physical health, mental health and the cost of health care utilization.**

H3: RIMO will have direct and indirect (via days of MAT treatment and days of opioid use) effects on: a) opioid-related fatalities, b) opioid use disorders symptoms, c) physical health, d) mental health, and e) cost of health care utilization.

Referral Only Control. During the phase 1 pilot, we collaborated with our study partners as well as the Illinois Opioid STR partners to develop a brochure that includes a list of MAT providers in Chicago, and their location, telephone number, hours of operation, adjacent bus lines, and type of funding accepted (e.g., Medicaid). In addition, the brochure includes a range of other SUD treatment options (e.g., residential or outpatient drug-free treatment), including office-based physicians who prescribe buprenorphine or other forms of MAT. This brochure is will be given to participants in both groups at the baseline assessment. Research staff will follow a script that does not include any statements regarding motivation for treatment. At present, based on our interviews with key informants and focus group with pilot study participants, there is currently no systematic method in place for referring individuals to MAT (or other SUD treatment) either from the first responders following administration of naloxone or at the EDs following their admission for opioid-related overdose. Hence, this condition represents more than the “usual care” in the community.

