## **2. Primary and secondary objectives and outcome measures**

The primary outcome measure for the study is the GAIN-Quick Version 3 (GAIN-Q3). The GAIN-Q3 includes 4-6 symptom count screeners that are correlated .9 or more with the 11 to 43-symptom version in the full GAIN. It also has cut points with excellent (~90%) sensitivity, specificity, and area under the curve (AUC) relative to the full GAIN in 9 problem areas related to substance use disorders, physical health, internalizing and externalizing mental health disorders, as well as school, work, stress, HIV risk behaviors/victimization, and crime/violence. The days of use measures have been validated against the Timeline Follow-back, collateral reports, and urine and saliva tests. The GAIN-Q3 also includes summary measures for health care utilization, functional impairment, quality of life, and life satisfaction. The GAIN-Q3 includes the behavioral health screener and health care utilization measures that have been recommended by NIH's Phenx common data elements as two of the most reliable, valid, efficient, and inexpensive tools in the field. At each follow-up, the Q3 follow-up will be supplemented with a) a section on overdose and naloxone experiences, and b)

symptom counts from the OUD scale. Table 2.1 crosswalks the key independent measures and secondary outcomes from the hypotheses to their definitions, reliability, data sources, and the specific aims they address.

Table 2.1. Crosswalk of Variables, Definition, and Aims	H1	H2	H3
Experimental Assignment: Based on computer-generated urn randomization, participants will be assigned to the referral only control group or the experimental RIMO condition.	R	R	R
MAT Time to Initiation: Days from index naloxone administration to the initiation of any kind of MAT, from treatment records.	O		
Length of Staying on Medication: Days between MAT initiation and discharge, from treatment records.	O		
MAT Days: Total days of MAT over 9 months from GAIN-Q3 and treatment records.	O	M	M
Time to Relapse: Days from randomization to next subsequent use of opioids or heroin based on GAIN Q3 follow-up interviews and urine tests.		O	
Opioid Days of Use: Days of opioids and/or heroin use summed over the GAIN-Q3 follow-up interviews.		O	M
Opioid Overdose: Number of opioid-related overdose[s] summed over the GAIN-Q3 follow-up interviews.		O	

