### 3. Inclusion and exclusion criteria

The study will target individuals who have received naloxone administered by first responders within the past week to reverse an overdose, but who have not entered into MAT. Inclusion criteria are: a) experienced an opioid overdose reversed with naloxone administered by first responders on a participating team within the past week, b) not in treatment during the past 30 days, and c) screen positive for an OUD. For logistical reasons, we will exclude anyone who is: d) under age 18, e) unable to speak and understand English, f) not residing in Chicago, or g) cognitively unable to provide informed consent.

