The first responders will follow their standard practices for obtaining contact information from individuals following naloxone administration (i.e., name, address, phone number). For those who are alert and oriented, first responders will ask one additional question of the participants, which is whether they are willing to be contacted by someone in a few days to see how they are doing and talk about available help. If they respond affirmatively, first responders will request their signature on a form indicating their consent to share their contact information with the study investigators who will contact them, optimally within 48-72 hours. Finally, all individuals, whether or not they consent to release their information, will be provided with a brochure listing MAT providers in the local community. Research staff will pick up the release and contact forms daily from each participating firehouse and police station and document the number of people who overdosed and received naloxone and who: a) agreed, b) were not alert and/or oriented and were not asked, or c) refused. The rate of consent/refusals will be monitored against the total number of daily naloxone administrations. We will look for patterns to consent/refusal and debrief with first responders about the process. Study partners will meet every other week during the recruitment phase to monitor recruitment, discuss challenges, and develop strategies to increase recruitment, if needed. Based on the research team's success on prior studies tracking and locating participants, we expect that research staff will successfully contact approximately 75% of participants by telephone or through direct outreach. As reported in the initial focus group, we expect that almost all will currently be using opioids or heroin. Upon contact, research staff will screen individuals for eligibility based on study inclusion criteria; if eligible, they will be invited to the research office to complete the informed consent and baseline interview and will be randomized. Transportation will be provided as needed.

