## **10. Statistical analysis plan**

Missing data. Participants will complete their baseline interview prior to randomization. Based on prior studies conducted by the applicants, it is expected that approximately 90% or more of the 3, 6, and 9-month post-randomization interviews will be completed. Among these completed interviews, prior studies conducted by the team indicate that less than 1% will have additional missing data on any of the core items required to test the study hypotheses. Multiple imputations will be used to replace the small amounts of missing data to allow the least biased estimate for each analysis. To further reduce potential bias, analyses will be rechecked by running them without missing data. If there are any clinically significant differences ( $d > |.2|$ ), a general latent variable framework will be used to analyze non-ignorable or systematic missing data that tests whether missing data is qualitatively different by condition.

Survival Analysis for Time to MAT Initiation and Time on Medication (Aim 1). The primary outcome is the days from randomization until the initiation of any kind of MAT. Relative to the referral only control group, the direct effects of RIMO on reducing the days from randomization to initiation of any MAT (H1a) and increasing the days on medication after initiation (H1b) will be evaluated with a Cox Regression model using IBM SPSS version 24 with random assignment to RIMO as the main predictor, as the investigators have done in earlier experiments. It will be examined after the point of randomization and after each follow-up interview. Survival analysis incorporates information about censorship (e.g., death, people who were not admitted to MAT within 9 months) and can incorporate covariates if needed. The output includes a case summary (e.g., missing data, other problems, descriptive statistics) and an evaluation of each term (e.g., beta, its standard error, Wald, its probability, the odds ratio, the 95% confidence interval for the odds ratio). The beta can also be converted to a Cohen's effect size *d*. All analyses will use an intent-to-treat approach (i.e., participants are analyzed as assigned regardless of their actual level of participation in RIMO). We will also conduct a secondary analysis of the time to MAT initiation after each RIMO checkup to understand the pattern over time as we have done with earlier experiments.

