Direct Effects of RIMO on MAT (Aim 1). Relative to the referral only control group, the direct effects of RIMO on reducing dropout and receiving more total days of MAT will be evaluated using a multilevel structural equation modeling (MSEM) with mixed effects in MPlus (version 7.4). The analysis will model observations (Level 1) nested within participants (Level 2), with participants modeled as a random factor anchored on the baseline version of the dependent variable. Randomization to RIMO will be modeled as a Level 1 predictor. We will check for the need to use models that adjust for counts or zero saturation.

Direct Effects of RIMO on Secondary Outcomes of Time to Relapse, Opioid Use and Overdose (Aim 2) and Death, OUD, Health, Mental Health, and Health Care Utilization (Aim 3). Relative to the referral only control group, the direct effects of RIMO on time to first relapse (H2) will be evaluated with a survival analysis similar to Aim 1 H1. It will be examined after the point of randomization and after each follow-up interview. The direct effects of RIMO on days of opioid use (H2), opioid overdoses (H2), opioid-related fatality (H3), symptoms of OUD (H3), physical health problems (H3), mental health symptoms (H3), and the cost of health care utilization (H3) will also be evaluated using a series of MSEM with mixed effects in MPlus modeled in the same way as above. Most of the above variables are relatively continuous, but we will check for the need to use models that adjust for counts or zero saturation. For opioid-related fatality (H3), we will define the dependent variable as dichotomous in MPlus (equivalent to using logistic regression).

Indirect Effects of RIMO (Aims 2 and 3). To evaluate indirect effects, we will determine the extent to which the direct effects of RIMO on the above dependent variables are changed by of days of MAT received (H2 & H3) and/or days of opioid use (H3) using the Preacher and colleagues framework for testing mediation in MSEM with REML in MPlus. Loss of statistical significance in the path coefficient from the intervention conditions to the other outcome variables would indicate full mediation; a reduction in the path coefficient would indicate partial mediation. Change will be evaluated using MacKinnon's joint-significance testing of the path *z*-scores with a Sobel test using a standard error based on bootstrapping and criteria of  $p < .05$  on the degree of change.

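### Time to relapse (H2a) in effect measures time to next opioid use, and its mediator, total MAT days over 9 months, includes days after the event

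*Combined protocol and SAP*

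**What the plan says.** - **Outcome.** Section 2, Table 2.1 defines time to relapse as "Days from randomization to next subsequent use of opioids or heroin based on GAIN Q3 follow-up interviews and urine tests". No period of abstinence has to come first.
- **Population.** Section 3 admits people whose overdose was reversed in the past week and who were "not in treatment during the past 30 days". Section 8 says of those contacted that "we expect that almost all will currently be using opioids or heroin".
- **Hypothesis.** In section 1, H2 states that "RIMO will have direct and indirect (via days of MAT treatment) effects on: a) time to relapse".
- **Mediator.** Table 2.1 defines MAT days as "Total days of MAT over 9 months from GAIN-Q3 and treatment records" and marks them as the H2 mediator. The paragraph on indirect effects in section 10 applies this mediator to the Aim 2 and Aim 3 outcomes and makes no exception for time to relapse.
- **Direct-effect analysis.** Section 10 analyses time to first relapse by survival methods like those for H1, and adds: "It will be examined after the point of randomization and after each follow-up interview". The same sentence appears for MAT initiation. There, a further analysis is announced separately and called secondary: "We will also conduct a secondary analysis of the time to MAT initiation after each RIMO checkup to understand the pattern over time".

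**The concern.** Relapse normally means a return to use after stopping. Here most participants have not stopped when the clock starts, and MAT can begin only after entry. The first event will often be ordinary continued use, before the main route by which RIMO is meant to work has begun. A hazard ratio near 1 could then be misread as no effect on relapse.

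The mediation test has a separate problem of time order. A day of MAT received after first use cannot have postponed that use, and it may partly be a consequence of it, for example if early use affects whether the person enters or stays in treatment. A path from 9-month MAT days to time to first use mixes the intended effect with its reverse.

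**Working it through.** The plan gives no event rate, hazard ratio or power for time to relapse, so there is no figure to reproduce. What follows shows direction and range under stated assumptions.

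**1. Pilot figures (section 1).** Mean MAT days at the 30-day follow-up were 11.2 (RIMO) and 0.76 (control). As shares of 30 days these are 11.2/30 = 37% and 0.76/30 = 2.5%, so on average about 19 and 29 of the 30 days were off MAT. This fits frequent use outside MAT but does not show how many people used before starting.

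**2. Chance that a RIMO starter uses before MAT.** Let the time to next use have mean g days and the time to MAT start have mean m days, both exponential and counted from randomization. Then p = m/(m+g). Assumed ranges are g = 1 to 4 and m = 3 to 10.

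**3. Share of RIMO MAT days after first use.** Starters who use first have all their MAT days after the event. Of those who reach MAT first, a share s stop use and contribute none, while the rest use soon after starting and contribute nearly all. With equal MAT days per starter, share = p + (1−p)(1−s). With s = 0.5:

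| g | m | p | share |
|---|---|---|---|
| 1 | 3 | .750 | .875 |
| 1 | 7 | .875 | .938 |
| 1 | 10 | .909 | .955 |
| 2 | 3 | .600 | .800 |
| 2 | 7 | .778 | .889 |
| 2 | 10 | .833 | .917 |
| 4 | 3 | .429 | .714 |
| 4 | 7 | .636 | .818 |
| 4 | 10 | .714 | .857 |

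Simulation of the same model (175 per arm, 270 days) gives .71 to .95 when starters stay on MAT to month 9, and .70 to .95 with a mean stay of 60 or 120 days. The result hardly depends on retention.

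It does depend on s. If every starter stops use (s = 1), the share equals p, .43 to .91. If a quarter do (s = 0.25), it runs from .429 + .75 × .571 = .86 to .909 + .75 × .091 = .98.

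**4. How informative the direct comparison is.** Assume 6% control uptake of MAT. The pilot odds ratio of 20.2 then gives odds of (.06/.94) × 20.2 = 1.29, so RIMO uptake is 1.29/2.29 = 56%. A weaker contrast of 40% vs 20% is also assumed. The simulation uses a two-sided 5% log-rank test from randomization, with half of starters stopping use and staying on MAT to month 9:

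| RIMO acts | Power, 56% vs 6% | Power, 40% vs 20% |
|---|---|---|
| only through MAT | 12–92% | 6–26% |
| also stops use in 10% of those who never start MAT | 53–99% | 54–74% |

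The loss of information is therefore conditional on how much of RIMO's effect runs through MAT.

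**The case against.** The strongest reply is that randomization is the correct intent-to-treat origin and that the plan chooses it. Table 2.1 counts from randomization, and section 10 models the analysis on Aim 1, where the main clock also starts there. H2 posits a direct effect as well, and section 8 describes non-MAT action plans for people who decline treatment, so RIMO could delay next use without MAT. Opioid use days (H2b) are tested too. All of this stands. It limits the point to the outcome's name and interpretation and to the mediator; it does not repair the mediator's time order.

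Three stronger readings are tempting and are not supported:

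- **That no origin is designated, so several results could each be claimed as H2a.** Table 2.1 and the parallel with Aim 1 make randomization the default. The sentence on later examinations may mean restarted clocks or only an updated analysis at each wave. The gap is a missing label and an undefined risk set.
- **That the main clock should start at month 3.** That origin requires no abstinence either: in a simulation under the same assumptions, 72–87% of participants used within 14 days of it. It also drops the first three months. With a mean MAT stay of 60 days and 56% vs 6% uptake, its power is 11–14%, against 11–87% from randomization.
- **That H2b and H2c escape the mediator problem.** They sum use days and overdoses over the same 9 months as MAT days, so time order is not established there either.

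**Conclusion.** The point holds in a limited form. As defined, time to relapse is time to next opioid use, and for many participants that will come before any MAT. *Many* is an inference from the entry criteria and the expectation of current use; the documents give no share. A reader might infer that the randomized comparison is biased. It is not: it is valid, but potentially uninformative about relapse to the extent that RIMO acts through MAT.

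The mediation fault is firmer. Total 9-month MAT days include days after the event whatever inputs are chosen, unless no one has MAT after first use. The size, about 70–95% of RIMO MAT days, rests on assumed use gaps, MAT delays and half of starters stopping use. Severity is low, because H2a is one component of a secondary hypothesis.

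**What to change.** 1. **Mediator (section 10).** Do not use total 9-month MAT days as the mediator for time to relapse. Either enter MAT as a time-varying exposure up to first use, built from the initiation and discharge dates in treatment records, or drop the H2a indirect test and rely on the other H2 outcomes. In the second case, state that MAT days and use days or overdoses summed over the same 9 months do not establish time order.
2. **Outcome (Table 2.1).** Keep randomization as the main origin, rename the outcome *time to next opioid use*, and state that a null result is not evidence of no effect on relapse.
3. **Later analyses (section 10).** Label the analyses after each follow-up interview as secondary, matching the label used for MAT initiation. Say whether the clock restarts. If it does, keep everyone randomized, by assigned group; restricting to people who are abstinent or on MAT would lose the randomized comparison.

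**Cost.** The change is wording in the analysis plan and uses data already planned. The H2a indirect effect is either given up or needs a somewhat more complex model. Because MAT receipt is not randomized, the time-varying estimate would remain observational, as the planned mediator path already is.

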In Phase 1 (R21), the study team worked with the CFD to train Emergency Medical Service (EMS) teams to obtain authorization for release of contact information from individuals after an overdose reversal. The experimental pilot study tested the feasibility of each step in the intervention protocol and compared individuals who were randomly assigned to receive either a treatment referral pamphlet or the RIMO intervention on treatment received at 30-day follow-up. Qualitative data was also obtained from a focus group with participants in the RIMO group. A total of 75 individuals who had received naloxone from EMS were informed about the study; 50 (67%) of these signed the authorization form and provided their contact information; 33 met with the study team, consented to participate, and were randomized. Compared to the control group, the RIMO group (n=16) had higher odds of receiving any treatment for opioid use (OD = 7.94) and any MAT (OR = 20.2); they received significantly more days of opioid treatment (15.2 vs. 3.4) and more days of MAT (11.2 vs. 0.76) relative to the control group (n=17; all p < .05). Qualitative data highlighted the core components of the RIMO intervention. The pilot study demonstrates the feasibility of partnering with EMS and using the RIMO intervention to address the challenges of linking and engaging individuals into MAT after opioid overdose. These findings have been submitted for publication ([name] et al., under review) and were used to refine the study design for phase 2.

In Phase 2 (R33), research staff will continue to work with the CFD's EMS division and CPD to identify people who have just had an opioid overdose reversed with naloxone, recruit them into the trial, randomize them to a passive referral (via a brochure) vs. the RIMO experimental group. Using the study recruitment and RIMO procedures refined in Phase 1, a total of 350 individuals will be recruited and randomly assigned to the "referral to MAT" control or to "RIMO". All participants will receive standardized assessments at baseline and 3, 6, and 9 months post-randomization. The study's aims and their associated hypotheses are:

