Follow-up. The team will implement [name] follow-up procedures and conduct assessments at 3, 6, and 9 months post-randomization. This model has reliably produced over 90% follow-up rates across studies involving over 70,000 participants of diverse characteristics over follow-up periods ranging from 3 months to 19 years. Steps include: (a) contacting all participants within 24-48 hours of study intake to collect additional locator information and mailing a schedule card for the next interview, (b) recording information in an MIS, (c) assigning each case to an experienced follow-up case tracker, (d) verifying locator data, (e) conducting outreach for unverified cases and discussing them at weekly meetings, (f) mailing thank-you cards to participants and collaterals, (g) scheduling follow-up appointments, (h) mailing 3 and 6 week post-enrollment flyers, (i) implementing returned-mail procedures, (j) calling participants 6 weeks before appointment to confirm date and location (phone vs. research office), (k) conducting outreach for unconfirmed cases and reviewing

them at weekly meetings, (l) completing follow-up interviews and scheduling next appointments, and (m) implementing a no-show protocol. Participants will receive a \$25 incentive upon completion of each interview (\$100 across). Progress will be monitored with daily management reports. These procedures will help maintain participant contact for individuals in both the RIMO and referral-only groups.

**Data Editing and Quality Assurance.** When possible, computer-assisted personal interviews will be conducted. The GAIN interview conducts range checks, makes simple and complex skips, and allows immediate consistency checks. If an interview needs to be done with paper and pencil (e.g., detention, jail, and hospital), the interviewer will field edit it followed by a second edit to verify that key fields are complete, provide feedback and/or get clarification of questions, and mark any missing/bad data. The Research Manager will review inconsistent or missing data with the interviewers. When the data are keyed, the computer system will again check for range and consistency across multiple items. Weekly management reports will be used to monitor performance and error reports will be reviewed weekly until there are no major problems (or when there is a new staff person), then monthly thereafter.

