## **12. Procedures to guarantee the accuracy and completeness of the dataset**

Drs. [name] and [name] will train and supervise research staff. Interviews are checked for completeness and relative to urine tests at office visits. All interviews will be digitally recorded and a random sample reviewed for quality assurance. Our QA process has previously produced consistently good psychometrics across staff, sites, and mode (in person vs. by phone). The GAIN electronic interview conducts range checks, makes simple and complex skips, and allows immediate consistency checks. If an interview needs to be done with paper and pencil (e.g., jail, hospital), the interviewer will field edit it followed by a second edit to verify that key fields are complete, provide feedback and/or get clarification of questions, and mark any missing/bad data. The Research Manager will review inconsistent or missing data with the interviewers. When the data are keyed, the computer system will again check for range and consistency across multiple items. Weekly management reports will be used to monitor performance and error reports will be reviewed weekly until there are no major problems (or when there is new staff), then monthly thereafter. All GAIN data will be checked for unexpected patterns of increased or decreased activity.

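### Time to relapse (H2a) is set for ordinary Cox regression in days, but the plan gives no way to date first use; unless the interview records one, the outcome is interval-censored

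*Combined protocol and SAP*

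**What the plan says.** - Section 2, Table 2.1 defines the outcome as "Days from randomization to next subsequent use of opioids or heroin based on GAIN Q3 follow-up interviews and urine tests". By contrast, MAT initiation in the same table comes from treatment records.
- Section 10: "the direct effects of RIMO on time to first relapse (H2) will be evaluated with a survival analysis similar to Aim 1 H1". The Aim 1 outcomes "will be evaluated with a Cox Regression model using IBM SPSS version 24 with random assignment to RIMO as the main predictor".
- Section 10 on censoring: "Survival analysis incorporates information about censorship (e.g., death, people who were not admitted to MAT within 9 months". Both examples are right censoring; interval censoring is not mentioned.
- Section 1: "All participants will receive standardized assessments at baseline and 3, 6, and 9 months post-randomization". No window is set around these time points.
- Section 1 (Follow-up) has participants called beforehand "to confirm date and location (phone vs. research office".
- Section 12: "Interviews are checked for completeness and relative to urine tests at office visits". Table 1.1 in Section 1 lists a urine test at every assessment, and Section 18 pays for each assessment as interview plus urine.
- The only opioid-use quantity that the plan describes from the interview is a count of days of use (Table 2.1).

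**The concern.** Cox regression in days needs a day for each event. A day count and a urine result at an interview show that use occurred since the last interview, but neither states the first day. For someone who denies use and tests positive, self-report supplies no date at all.

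An analyst without a rule would probably date the event to the interview that revealed it, to the scheduled wave, or to the interval midpoint. Interview or wave dates blur a real difference in time to use. Interview or midpoint dates also make the hazard ratio depend on when people were interviewed: the arm interviewed later appears to relapse later.

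Section 8 expects nearly everyone reached to be using opioids, so most first-use events would fall before the 3-month interview. Only RIMO participants have Linkage Manager contact 2-3 times a week and linkage sessions at the follow-up points, so a few days' difference in interview timing is conceivable.

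**Working it through.** The plan gives no event count, hazard ratio or power for time to relapse, so there is no figure to reproduce. The check is by simulation.

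**From the documents:** 175 per arm; interviews at about days 90, 180 and 270; 94% completion per wave (Section 4; used in steps 2 and 3); two-sided 0.05.

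**Assumed:** exponential time to first use; a stated proportion using by day 90; normal scatter of interview dates, SD 7 days unless stated; RIMO interviewed later by a stated number of days; Breslow handling of ties in the Cox model.

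**1. Why a few days matter.** The hazard is λ = −ln(proportion use-free at day 90)/90.
- 60% using: −ln(0.40)/90 = 0.0102 per day, mean 98 days.
- 85% using: −ln(0.15)/90 = 0.0211 per day, mean 47 days.

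A 3-day shift is 3/98 = 3% to 3/47 = 6% of mean time to use, but 3/7 = 0.43 SD of the interview date. When events carry the interview date, the second scale governs.

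**2. No true effect** (600 runs per cell). Entries are mean hazard ratio, RIMO vs control, and false-positive rate:

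| Use-free at day 90 | RIMO later by | Cox, interview date | Cox, true first-use date | Interval-censored model |
|---|---|---|---|---|
| 10% | 0 days | 1.00, 5.3% | 1.00, 5.2% | 1.00, 5.5% |
| 10% | 3 days | 0.83, 40% | 1.00, 5.3% | 1.00, 4.7% |
| 10% | 7 days | 0.65, 98% | 1.00, 6.7% | 1.01, 5.7% |
| 30% | 3 days | 0.88, 19% | 1.01, 5.5% | 1.01, 4.5% |
| 30% | 7 days | 0.75, 75% | 0.99, 5.3% | 0.99, 5.7% |
| 60% | 3 days | 0.91, 12% | 1.01, 4.7% | 1.01, 4.8% |
| 60% | 7 days | 0.79, 48% | 0.99, 4.7% | 0.99, 5.5% |

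Midpoint dating is also affected: 14-96% false positives at 7 days. A separate run at 60-85% use by day 90 (15-40% use-free) gave 17-43% at 3 days and 61-98% at 7 days with interview dates.

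**3. Dependence on scatter** (30% use-free, 3-day shift, interview dates): 77% for SD 3, 19% for SD 7, 9% for SD 14. The plan does not limit the scatter.

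**4. True hazard ratio 0.70, no timing difference, 60-85% use by day 90:**
- Cox on interview or wave dates: hazard ratio 0.73-0.86, power 10-80%.
- Complementary log-log by window: about 0.70, power 86-89%.
- Cox on exact dates: power about 90%.

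The last figure agrees with Schoenfeld's formula, power = Φ(√(D/4)·|ln HR| − 1.96), ignoring missed interviews.
- 60% using by day 90: use-free at day 270 is 0.40³ = 0.064 in control and 0.064^0.70 = 0.146 in RIMO. D = 175 × (0.936 + 0.854) = 313. √(313/4) × 0.357 − 1.96 = 1.20, or 88%.
- 85% using: 0.15³ = 0.003 and 0.019. D = 175 × (0.997 + 0.981) = 346. √(346/4) × 0.357 − 1.96 = 1.36, or 91%.

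**5. Interview mode** (assumed: self-report sensitivity 70-85%, urine detection 70%, office attendance 60-70% in control and 90% in RIMO, no timing shift): hazard ratio 1.03-1.12, false-positive rate 0-6%. This is a minor effect.

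**The case against.** Three stronger readings are tempting, and the documents support none of them.

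- **That the sources show only that use occurred since the last interview.** The plan does not list every interview item, so a first-use date item may exist undescribed. The outcome is defined in days, which suggests that a dated quantity was intended. Even the day count bounds first use: 60 days of use in a 90-day window starting at randomization puts it no later than day 90 − 60 + 1 = 31. With true dates the timing bias disappears (step 2).
- **That urine exists only at office visits.** Section 12 describes a quality check at office visits. Table 1.1 and Section 18 tie urine to every assessment. Phone interviews are allowed, so the sections need reconciling, but they do not establish missing urine.
- **That the arms differ in interview timing or mode.** Schedule and tracking are common to both, and interviewers are blind to assignment. With no shift, even interview-dated Cox holds its error rate (4.5-5.3%).

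Two further objections stand in part. False-positive rates depend heavily on the assumed scatter. The log-length offset assumes a constant hazard within a window; with a front-loaded hazard (Weibull shape 0.4, assumed), the null hazard ratio was 0.96 for a 7-day shift and 0.92 for 14 days. That is imperfect, but much closer to 1 than interview-dated Cox.

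None of this supplies a dating rule, or a date for denied-but-positive cases.

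**Conclusion.** The concern holds conditionally. As written, the plan applies a right-censored Cox model in days to an outcome drawn from three assessments about 90 days apart, without a first-use date item, a dating rule or an interview window. At least the denied-but-positive cases are interval-censored.

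If no first-use date is recorded, the cost arises even when interview timing is the same in both arms: attenuation toward the null and lost power (step 4). The extent of this under wave dating depends on the tie method, which the plan does not name. A false effect needs, in addition, an arm difference in timing, and none is documented. Its direction would follow the timing: later RIMO interviews would look like benefit, earlier ones like harm.

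This concerns one secondary outcome, but H2a is a named hypothesis and the remedy is cheap. The plan should be changed before analysis.

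**What to change.** In Section 10:

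1. Analyse H2a with a discrete-time complementary log-log model, or another interval-censored model, over the 0-3, 3-6 and 6-9 month windows. Use actual interview dates, window-specific intercepts and log window length as offset. The RIMO coefficient is still a log hazard ratio.
2. If first-use dates are recorded, name the item, use those dates, and treat denied-but-positive cases as interval-censored between interviews.
3. Treat an absent urine result as missing, not negative. The existing multiple-imputation rule was written for small amounts of missing data, so report how many results it has to cover.
4. Reconcile Section 12 with Table 1.1 and Section 18 on when urine is collected.
5. Report interview timing and mode by arm.

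**Cost:** mainly SAP wording. The plan does not say that interview mode is stored as data, so a field may be needed. There is a small loss of precision if exact dates exist and are not used, and the offset is only approximate if the hazard is front-loaded within a window.
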